Globally, leading causes of death among children one month to 5 years old are pneumonia, diarrheal disease and malaria which are treatable early in the disease-course with low-cost medications. However, these diseases can progress to emergencies when access to care is delayed, especially in low- and middle- income countries (LMICs). In response, our team has designed a telemedicine and medication delivery service (TMDS) called MotoMeds to overcome barriers to seeking care. We target the nighttime period when barriers to accessing care are highest. Our strategic plan is to design, deploy and evaluate MotoMeds through the improving nighttime access to care and treatment (INACT) studies. The TMDS was initially deployed in Haiti and now will be evaluated for generalizability and portability in Ghana. In Ghana, we have initiated a formative needs assessment (INACT1-G) to inform the design and approach of the pilot implementation of the TMDS (INACT2-G). The study objectives are to assess clinical safety and logistical feasibility. The study population is an urban slum within Accra and the enrollment period is nine months. The workflow consists of parents/guardians calling the TMDS on their child's behalf, Emergency Medical Technicians (EMTs) referring severe cases to emergency services, EMTs performing a phone assessment for non-severe cases, and EMTs travelling to the household to perform an exam and deliver protocolled medications for cases within the delivery zone. Eligibility criteria includes patient participants aged 0-10 years old with medical problem, parent/guardian participants calling on behalf of a patient participant, and TMDS staff aged 18 years and older. Written consent/assent will be obtained from patient and parent/guardian participants receiving a household visit. Parent/guardian participants who do not receive a household visit and TMDS staff will be

offered a waiver of documentation of consent. Estimated enrollment is up to 1,365 child and parent/guardian participant pairs, 15 call center EMTs, 10 delivery drivers, and 3 on-call physicians. Clinical safety will be evaluated through guideline adherence, congruence analysis between call center and in-person assessments, and clinical status at 10 days. Feasibility will be evaluated in terms of logistical data, parent/guardian feedback, and TMDS staff feedback.

#### 4. Background

**4.1 Pediatric health and healthcare.** Pneumonia, diarrheal disease, and malaria are the first, second, and third leading causes of mortality for children between one month and 5 years of age globally. Oral amoxicillin for bacterial pneumonia, oral rehydration solution for dehydration from diarrheal disease, and artesunate-amodiaquine for malaria can reduce mortality rates by 32%, 93% and 99.7%, respectively. However, these treatments are most effective when administered early after symptoms start, which is difficult when healthcare access is limited, especially at night. Delayed treatment, especially in children, can result in rapid progression to an emergent state. In LMICs emergency care is considerably more difficult to access and more expensive than pre-emergency care; thus emergencies must be prevented in order to decrease pediatric mortality. The WHO/UNICEF action plan for Ending Preventable Child Deaths calls for innovation within the domains of “delivery strategies, overcoming barriers to interventions and better ways for implementation”.

Since the COVID-19 pandemic, telemedicine has gained accelerated interest as an innovative approach to improve access to care. By improving clinician efficiency and accessibility, telemedicine has the potential to overcome workforce as well as distance barriers.

Successful pediatric use cases in LMICs include a virtual clinic for pediatric ambulatory surgical patients in Egypt and a telemedicine service for pediatric cancer and blood disorders in the Caribbean. However, the need for physical assessments limits what can be accomplished via telemedicine alone. A systematic review of interventions for improving access to healthcare for children under 5 in LMICs found “delivery of services close to home” was one of two interventions that was consistently associated with increased healthcare utilization. Accordingly, community health worker programs (CHWPs) continue to gain prevalence. CHWPs train community leaders to deliver healthcare resources directly to households in their neighborhood. These programs have been found to decrease both disease prevalence and mortality in LMICs. However, such programs are largely limited to the daytime.

The rise and success of community paramedicine programs exemplifies the potential of 24-7 telemedicine and medication delivery services. Community paramedicine is an evolving healthcare model in which EMTs operate in expanded roles to provide primary care to low-resource communities. The scope of community paramedicine practice varies by settings but often includes education, vaccination, and basic medication/fluid administration. Community paramedicine programs have been shown to effectively decrease emergency department visits through the provision of preventative and chronic care services in high income countries. The potential for telemedicine and medication delivery services to avert emergencies through the provision of acute care services in LMICs remains to be realized.

**4.2 Health and healthcare in Ghana.** The Ghanaian pediatric population could benefit from improved acute care services. The Ghanaian National Ambulance Service (NAS), a nationwide Emergency Medical Services (EMS) agency, works to provide timely emergency care. The NAS has prioritized EMS through the development of a Paramedic & Emergency Care Training School, operation of 297 EMS stations, and purchase of 307 new ambulances. However, the endeavor has exposed unanticipated costs that limit sustainability and scalability. Both NAS personnel and the Ghanaian public express concern over NAS resources and response. Currently a major challenge is how to prevent and manage pre-emergency cases that consume resources intended for emergencies.

To meet this need, Ghana Health Services manages a robust network of CHWPs. CHWPs have worked under the National Expanded Programme on Immunisation (EPI) to increase complete vaccination coverage for children 12-23 months from 85% in 1998 to 95% in 2014. Further, CHWPs have been found to be instrumental in treating pediatric acute illnesses such as pneumonia, diarrhea, and malaria in Accra and Northern Ghana; however, progress is insufficient.

Ghana's U5M rate is 48 per 1,000 live births with malaria, acute respiratory illness, and diarrheal disease accounting for 20%, 13%, and 8% of the U5M rate, respectively. Pediatric care in Ghana is compromised by a low level of general health education, shortage of healthcare personnel, and limited pediatric health facilities. The ratio of medical doctors to population is 1: 9,434. The 2014 Demographic and Health Survey found 43% of adult women—many mothers—were dissatisfied with primary care services.

**4.3 Clinical considerations in Ghana.** The high burden of malaria poses unique challenges to assessing and treating pediatric patients with fever. Conventional and point of care diagnostics play an important role. With respect to malaria, diagnostic modalities include polymerase chain reaction, smear microscopy, and rapid diagnostic testing. While polymerase chain reaction and smear microscopy are more sensitive than rapid diagnostic testing the need for conventional laboratory capabilities limits their use in point-of-care testing in low-resource settings. Performance metrics for rapid diagnostic testing vary widely up to 98% sensitivity and 92% specificity. With respect to acute respiratory infection, diagnostic modalities include imaging, lung function tests, culture, and polymerase chain reaction. Rates of coinfection among outpatient febrile children under 10 in Tanzania were found to be frequent, with viral and bacterial co-infection being most common, but also co-infection of parasitic and bacterial and/or viral origin. However, rates of single agent as well as dual agent infections in our study population are unknown.

**4.4 Feasibility Studies.** Interventions must be assessed for feasibility to determine whether scaling and comprehensive evaluations are justified. Feasibility studies focus on development of implementation strategies and refinement of research methods. Feasibility studies may be fixed—rigid in design—or flexible—allowing for changes during the course of the study. Conventional feasibility metrics for healthcare interventions include demand, implementation, integration, adherence, cost-effectiveness, clinical safety, and acceptability. However, there exists little guidance pertaining to feasibility thresholds. Rather, the theory and application of feasibility thresholds is widely questioned with the only

consensus being that feasibility thresholds must be determined realistically with attention to circumstance.

## **5. Specific Aims:**

**Aim I:** Assess the clinical safety of a nighttime TMDS in a prospective cohort pilot study of pediatric patients 10 years and younger. Paired exams will be performed at the call center (virtual) and at the household (in-person).

- The primary objectives are to determine the rate of guideline adherence at the call center (primary outcome measure) and household as well as evaluate congruence between call center and in-person assessment and determine clinical status at follow-up at 8-12 days.

**Aim II:** Evaluate the feasibility of the TMDS model with respect to patients.

- Logistical data on patient workflow will be collected (duration of call, time to delivery). Data will be analyzed against benchmarks set in formative research (call duration < 25 minutes and time to delivery < 2 hours).
- Parent/guardian feedback will be collected on the clinical, cost and quality aspects of the TMDS. Both quantitative and qualitative data will be analyzed to identify strengths and weaknesses of the TMDS design.

**Aim III:** Evaluate the feasibility of the TMDS model from the perspective of the staff.

- Data will be obtained from EMTs, drivers and on-call physician participants by questionnaires and focus groups. Domains of inquiry are clinical decision making, formulation of medications, communication with team members and households, and opportunities for improvement.
- Data will be transcribed, evaluated for themes using an inductive code, and summarized for strengths and weaknesses of the TMDS design.

## 6. Research Plan:

### 6.1 Definitions

**ARI:** Acute respiratory infection defined as the presence of fever and cough.

**EMT:** Emergency medical technician trained to provide emergency medical services.

**Household (HH):** A group of two or more individuals living in the same structure and share at least one daily meal

**INACT: Improving Nighttime Access to Care and Treatment.**

**INACT1-H:** Survey assessment in Haiti

**INACT2-H:** Initial TMDS implementation in Haiti

**INACT1-G:** Survey assessment in Ghana

**INACT2-G:** TMDS implementation in Ghana

**RDT:** Rapid diagnostic test.

**Telemedicine and Medication Delivery Service (TMDS):** A service offering phone-based assessments and treatment plans as well as household medication delivery.

**6.2 Study design:** Prospective cohort study (pilot).

**6.3 Population** The population of this study will include residents in or approximate to the adjacent communities of Jamestown and Usshertown within Greater Accra (Figure 1).

Jamestown and Usshertown are urban communities together known as Ga Mashie or Old Accra. Due to word of mouth, participants residing outside the study area may contact the TMDS; they will receive advice without corresponding delivery/household visits.

Accra Metropolitan, the District in which Jamestown and Usshertown are located, has a youthful population; approximately 20% of the population is under the age of 10. Ghana's under-5 mortality rate is 48 per 1,000 live births, with 57.1% of the population having access to satisfactory primary care. Ghana ranks 133 out of 180 on the Flourishing Index.

**6.4 Recruitment** The TMDS (e.g. 'MotoMeds nighttime healthcare for children') will be advertised to targeted communities within the study area. It will be promoted through flyers in an incremental manner at health facilities, schools, religious institutions, etc. as a service for families needing access to non-emergent healthcare for children 10 years and younger during the night. Messaging will clarify that the TMDS is a pilot initiative with a 9-month trial

**Figure 1.** Approximate study area comprised of Jamestown and Usshertown

period. In addition, audio messaging (radio and public announcements) may occur; content will be similar to that in the written advertisements. Ghana Health Services and local health promoters may assist with advertising efforts. Participants from INACT1-G (survey assessment, ongoing) will be actively notified of the service by phone; INACT1-G participants are consented to a 1-year follow-up period and/or follow-up until the post-study analysis has finished.

## 6.5 Inclusion criteria and enrollment estimates

### 6.5.1 Patient participant

#### *Inclusion criteria:*

1. Patient must be 10 years of age or younger
2. Has a medical problem
3. Provides written assent (10 years and household visit).

#### *Exclusion Criteria:*

1. Patient older than 10 years
2. Does not have a medical problem.
3. Medical problem involves physical trauma or mental health.
4. Refusal of assent (10 years and household visit).

### 6.5.2 Parent/guardian participants

[figure not shown]
#### *Inclusion criteria:*

1. Calls MotoMeds during operating hours
2. Parent/guardian of a patient participant meeting inclusion criteria
3. Provides written consent (household visit) or waiver of consent of documentation (no household visit).

#### *Exclusion Criteria:*

5. No consent/waiver of documentation of consent
6. Corresponding child participant does not meet inclusion criteria

*Enrollment estimates:* Enrollment will be determined by the number of eligible patient and parent/guardian participants that contact MotoMeds call center. Based on staff capacity, advertising will be controlled to target 3-5 patients per night. As such, a minimum of 819 and a maximum of 1365 patient and parent/guardian participant pairs will be enrolled. We estimate that loss of follow up at 8-12 days will be 10% (Figure 2). Repeat patients within

**Figure 2.** CONSORT recruitment, enrollment, and analysis figure for patient participants.

30 days will be excluded from analysis; other repeat patients will be considered unique participants.

### **6.5.3 TMDS staff participants.**

*Inclusion criteria:*

1. Age 18 years and older.
2. TMDS staff member.

*Enrollment estimates:* Call center EMT enrollment is estimated to be 5 to 15. Driver enrollment is estimated to be 5 to 10. On-call physician enrollment is estimated to be 1 to 3.

## **6.6 Consent/Assent**

### **6.6.1 Patient participants receiving a household visit**

Written assent will be obtained from patient participants aged 10 years. Participants unable to sign may assent via fingerprint. Explanation of informed assent procedures may be obtained in English (official language of Ghana) or another locally spoken language (ex: Ga) in which the EMT obtaining consent and the participant providing consent are fluent as is common research practice in Ghana given that the Ga language is seldom written (see Gamada Letter of Support).

### **6.6.2 Parent/guardian participants receiving a household visit**

Written consent to participate will be obtained in English from the parent/guardian of each patient who receives a household visit; all genders, including pregnant mothers will be included. Participants unable to sign may consent via fingerprint. Explanation of informed consent procedures may be obtained in English (official language of Ghana) or another locally spoken language (ex: Ga) in which the EMT obtaining consent and the participant providing consent are fluent as is common research practice in Ghana (see Gamada Letter of Support).

### **6.6.3 Parent/guardian participants not receiving a household visit**

For parent/guardian participants that are not receiving a household visit due to danger signs present, met capacity, or failed/declined delivery, a waiver of documentation of consent will be presented at the time of the initial call or at the time of the follow-up call (either 24-hour or at the 8-12-day follow-up call). The rationale for the waiver of documentation of consent is that the survey questions pose no more than minimal risk and written consent is not logistically feasible. Explanation of informed consent procedures may be obtained in English (official language of Ghana) or another locally spoken language (ex: Ga) in which the EMT obtaining consent and the participant providing consent are fluent as is common research practice in Ghana (see Gamada Letter of Support).

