### **6.6.4 TMDS staff participating in questionnaire/focus group**

A waiver of documentation of consent to participate will be obtained in English from MotoMeds staff members. The rational is that staff focus groups are likely to be performed over Zoom or a similar video-conferencing software.

[figure not shown]
**6.7 Workflow.** The call center will operate during the nighttime (exact hours will be determined from INACT1-G). Staffing will be elastic to the needs of the call center case volume. If there are multiple calls at one time, the call center will be staffed to field 1-2 calls at a time. If the call volume is greater than expected, the calls will be placed on hold until a call center EMT is available. If the delivery/household visit volume is greater than the capacity to respond, the contingency plan is as follows: A restriction ('cap') will be activated such that no more than 3 participants can be waiting for a delivery at one time. If there are more than 3 participants waiting, the participants will receive advice by phone and will not receive a delivery/household visit. These cases will be recorded as study data. If volume consistently exceeds the planned capacity, the number of staff (EMTs and drivers) will be increased as funding allows.

Call intake will be managed by the HIPAA-compliant call center software Twilio and case dispatch will be managed by the Beacon Crisis Response. Dispatch alerts via Beacon will include the caller's name, phone number, location, as well as patient complaints; Beacon is also HIPAA-compliant.

Severe cases, certain fever cases and cases with unsuccessful deliveries will be contacted by phone within 24 hours (maximum of 2 attempts over the course of another 24 hours) and all participants will be contacted (maximum of 3 attempts) at 8-12 days to ascertain disposition, if additional care was sought, and qualitative feedback about the service. Responses will be recorded on paper forms and/or directly into REDCap.

Focus groups with TMDS staff will be performed to determine service usability and acceptability from an operational perspective.

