**6.8 Clinical procedures.** The clinical guidelines will adhere to Ghanaian and WHO standards of care and have been developed in collaboration with Ghanaian and US government experts in malaria. During each call it will be disclosed that the call center objectives are to provide pre-emergency health support and conduct research to improve nighttime access to standard of care. To identify emergency cases, triage will occur at the level of the call center EMT (mild, moderate, and severe, see clinical guideline appendix) and leverage WHO derived danger signs for life-threatening illness. If the EMT identifies a

**Figure 3. MotoMeds Workflow.** Follow-up calls will be placed within a range of 8-12 days.

danger sign at the call center or household and thus triages the case as severe, the EMT will advise the patient to seek care at a medical facility and will offer to refer the patient to NAS emergency dispatch (for an ambulance to be dispatched if so desired by the caller).

The clinical guidelines define the clinical scope of the TMDS (also discussed above in the inclusion criteria section). This study is being conducted in an area with high pediatric morbidity and mortality from malaria. Our approach is to follow WHO standards of 'test and treat'. Febrile patients will all be tested with a commercial RDT for malaria. RDT positive patients will be treated with antimalarials. Caregivers of RDT negative patients who do not have another source of their fever will receive a next-day follow-up phone call.

A follow-up call will be placed within 24 hours for severe cases and for those mild/moderate cases with a fever without source and a negative RDT as described above. If a case is triaged as mild or moderate (no danger signs identified), local EMTs will conduct a phone-based assessment. If the patient household is outside the delivery zone, consult alone will be provided as a clinical case; the data from these encounters will not be recorded as study data, given that these patients represent a different patient population. Therefore, they will not receive a waiver of informed consent or follow-up call. If the household is inside the delivery zone (Jamestown/Usshertown), the EMT will generate a treatment plan and medications/fluids will be delivered to the household. A follow-up call will be placed at 8-12 days, ideally at 10 days. In the INACT2-G pilot study, all patient participants will receive a paired in-person exam at a household visit.

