The clinical approach will be standardized across EMTs at the call center and at the household. Standardization will occur through paper and/or digital guideline generation for the common chief complaints identified in INACT1-G. Each call center assessment will produce a treatment plan that may include direction to seek emergency care, clinic follow-up, fluids, and/or basic medications (see clinical guideline appendix). The clinical guidelines and workflow (Figure 3) were localized to standards of practice (e.g. selection of guideline-recommended antimalarial medications) and epidemiology (high malaria burden).

Neither the ability to receive care nor the type of care will be affected by the decision to participate in the study. If a family declines to consent to inclusion in the research study, evaluation/care will be provided as outlined in the clinical guidelines. The data from this encounter will not be recorded as study data.

All household medication/fluid deliveries will be accompanied by an EMT with the intent that the medication handoff will happen after the EMT examines the patient and any necessary adjustments to the treatment plan are made. If patients are excluded from participation in the study, standard of care information will be conveyed and/or indications for seeking emergency care. The data from this interaction will not be recorded as study data.

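### Callers without a household visit may first be asked for the consent waiver at the 24-hour or 8-12-day call, so study entry and adverse-event counting can depend on contact and agreement after the outcome

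*Combined protocol and SAP*

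**What the plan says.** The abstract names three safety measures: "Clinical safety will be evaluated through guideline adherence, congruence analysis between call center and in-person assessments, and clinical status at 10 days".

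Section 6.6.3 covers families inside the delivery zone who get no visit because of danger signs, a reached capacity limit, or a failed or declined delivery. For them, "a waiver of documentation of consent will be presented at the time of the initial call or at the time of the follow-up call", and the follow-up call may be the 24-hour or the 8-12-day one. No order of preference is given.

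Section 6.5.2 makes written consent (visit) or a waiver (no visit) an inclusion criterion, and lists as an exclusion "No consent/waiver of documentation of consent". Its enrollment estimates plan for 10% loss at 8-12 days.

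Under section 6.7, "Severe cases, certain fever cases and cases with unsuccessful deliveries will be contacted by phone within 24 hours", with at most two attempts. The 8-12-day call, with at most three attempts, is where disposition is ascertained. Callers turned away by the capacity limit are recorded as study data but are not named for the 24-hour call.

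Where a family declines consent, section 6.8 says "The data from this encounter will not be recorded as study data". Section 6.11 keeps data on refusers only to count exclusions and reasons. Section 7 counts serious events that arise between enrollment and the 8-12-day call, and sets a suspension threshold of 2 deaths per 200 enrolled.

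**The concern.** If a family is first asked at the call that also collects the outcome, membership of the cohort is settled after the outcome has occurred. It then depends on two things the outcome may influence: whether the family can be reached and whether it agrees.

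This matters most for children triaged as severe by phone. Section 6.19 states that no in-person data are obtained on emergent patients, so follow-up calls and serious-event reports are their only outcome evidence. Callers turned away at capacity are mild or moderate cases and matter less, but for them the outcome call can be the first offer.

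The timing also touches safety monitoring. Section 7 ties the event window to enrollment, and the plan does not say on which date a family with a late waiver is enrolled.

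**Working it through.** **Following the rules through for a deferred family**

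1. *Reached, declines late.* No waiver, so excluded (6.5.2). The refusal is counted (6.11), but the child is not in the 8-12-day status or mortality results.
2. *Never reached, so never asked.* No waiver, so excluded on a literal reading of 6.5.2, and the initial-call record leaves the adherence analysis too. Had the same family given the waiver at the first call, it would count as lost to follow-up. Section 6.11 speaks of refusal only, and the visible text does not say how the never-asked are counted.
3. *Serious event, then a late waiver.* The section 7 window opens at enrollment and closes at the 8-12-day call. If enrollment dates from a waiver given at that call, the window has no length. Of two deaths in 200, one that preceded a late waiver would not count, and the threshold of 2 would not be met.

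An offer at 24 hours comes before the 8-12-day status, so it follows the outcome only for early deaths or deterioration. The 8-12-day offer is the clear case.

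**Effect 2 in numbers**

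Inputs from the plan: 819 enrolled (6.12), 10% loss (6.5.2), and one death in 391 in the earlier Haiti service (7). Section 7 expects two deaths among 891. This reproduces: 891/391 = 2.28, and 819/391 = 2.09, both about two.

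Assumptions: 10% are unreachable at 8-12 days whatever the group; a share s of eligible callers is first asked at that call; nobody reached declines; two deaths are known. The plan does not give s, so 5% to 20% is an assumed range.

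- Eligible callers: E = 819 / (1 − 0.10s)
- Never enrolled: 0.10 × s × E
- Lost among the enrolled: 0.10 × (1 − s) × E
- Reported loss: 0.10 × (1 − s) / (1 − 0.10s)
- Worst-case mortality: (2 + never enrolled + lost) / E

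| s | Eligible | Never enrolled | Lost, enrolled | Reported loss | Total unknown | Worst case |
|---|---|---|---|---|---|---|
| 0% | 819.0 | 0 | 81.9 | 10.0% | 81.9 | 10.2% |
| 5% | 823.1 | 4.1 | 78.2 | 9.5% | 82.3 | 10.2% |
| 10% | 827.3 | 8.3 | 74.5 | 9.1% | 82.7 | 10.2% |
| 20% | 835.7 | 16.7 | 66.9 | 8.2% | 83.6 | 10.2% |

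(Entries are rounded separately.) Total unknown is 10% of eligible callers in every row. Within the deferred group, reported loss is 0% by construction, because only families who were reached can enter. A bound computed from the enrolled alone at s = 20% would read (2 + 66.9)/819 = 8.4%, which is why the never-asked need to be added back.

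The share of initial-call records that leaves the adherence analysis by this route is 0.10 × s, or 0.5%, 1.0% and 2.0% of eligible callers.

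Effects 1 and 3 cannot be calculated: the documents give no rate of late refusal, no share of callers without a visit and no risk for that group.

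**The case against.** The strongest case against is that timing changes little. For a family never reached, 8-12-day status is unknown whether or not a waiver was given earlier; only the label on the missing value differs. If deaths and survivors are captured equally, the mortality proportion is not biased. This stands, and it confines any outcome bias to late refusals and to events before a late waiver.

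Flexibility also has good reasons. Failed deliveries are known only later, and danger-sign calls are emergency referrals. Section 6.6.3 already allows the first call, and severe cases have up to three occasions to be asked. This limits the problem, but nothing tells staff to use the first occasion where they can.

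Figure 2 is not shown and may say how never-asked callers are counted, so their omission cannot be asserted. Section 6.11 times data collection from the initial call, so section 7 may intend the same starting point; it does not say so.

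Two stronger readings are tempting. A reader might infer that late waivers widen the mortality bound, with unasked families added on top of the planned loss. With equal reachability that counts the same families twice, as the table shows. A reader might also infer that mortality will be understated, since one missing death weighs heavily when about two are expected. That sensitivity applies to any cause of loss, and the documents do not establish which way late refusal would act.

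**Conclusion.** The concern holds in a limited form. As written, the plan lets entry for in-zone callers without a visit depend on contact and agreement after the outcome, and leaves the start of their adverse-event window undated. The calculable effect is modest: reported loss of 9.5%, 9.1% or 8.2% instead of 10% under the stated assumptions, concentrated in the group without visits, with total unknown status and the worst-case bound of about 10.2% unchanged. The primary outcome is little affected through non-contact.

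The outcome-specific part, from late refusals and from events before a late waiver, has unknown size and direction. It is still worth correcting, because it falls partly on children triaged as severe and bears on a suspension threshold of only two deaths. Confidence is medium: late offers are permitted, not required, and Figure 2 could not be seen.

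**What to change.** (a) In section 6.6.3, offer the waiver at the initial call where this does not interfere with referral, keep the follow-up calls as a fallback, and record when the waiver was obtained.

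(b) Subject to ethics committee agreement, report de-identified counts of eligible callers without a visit who declined or were never asked, by triage category. Include the never-asked with the lost when stating how many have unknown 8-12-day status. Families who decline stay out of the study data, as section 6.8 requires.

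(c) In section 7, for callers who give a waiver at any time, count the serious-event window from the initial call.

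The cost is protocol wording, one extra recorded item, ethics agreement on the counts and a small table, with no extra visits or staff. Section 6.8 already provides that "During each call it will be disclosed that the call center objectives are to provide pre-emergency health support and conduct research", so the waiver adds to an existing step. The downsides are a slightly longer first call and a slightly higher reported loss to follow-up. Earlier asking makes unreached families visible as lost; it does not recover their outcomes.
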